## Study Protocol

The second year of "A Trauma-Informed Approach for Positive Youth Development for Montana Students" will continue in the same format as winter 2020, but with 35 participants in an experimental group, along with 20 students in a control group within the same school and enrolled in classes by the same physical education teacher. District leaders wish to hold the study during the Jan-March 2021 window, as this timeframe has shown a historical spike in inappropriate student behaviors and absenteeism. Twice weekly 45-minute sessions during the 8-week intervention period will occur within two physical education classes in order to draw enough participants to gauge statistical significance with resulting data; a third physical education class with the same teacher will serve as the control group for the study, therefore creating 3 gym class clusters, which will allow for computer-generated randomization. Instead of individuals being randomly assigned, gym class clusters of individuals will be randomly allocated to intervention groups. Control group participants will also be offered 8 weeks of yoga after the study concludes.

Student incentives for at least a 75% attendance record in the experimental group include receiving a Fitbit Inspire HR for the study to track their physical health data and students will retain these to encourage healthy exercise and sleep patterns following the study. Teacher incentives for completion of surveys include classroom supply money (funneled through school administration). Gift cards will be provided to parents/guardians who complete the surveys about their child; these will be disseminated by school officials for parents to pick up at the high school, or they may be mailed by the PI on request. Control group participants will also each receive Fitbit Inspire HR upon completion of all pre- and post-survey measures as an incentive.

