To prepare for pilot study year 2, feedback has been gathered from the school district, teachers, and students via focus groups and email communications to assess the burden from the various assessment instruments and participation in the pilot. Assessment measures listed below comport with this feedback. Retention and satisfaction of participants, as measured by survey instrumentation from year 1 has indicated the need for an ongoing partnership with the school district and an expansion to additional high school physical education classes (8-week intervention, n=35). During year 2, the study will compare results between the experimental group and a new 20-participant control group, which will be located within the same school setting. The intervention’s effectiveness for youth mental and physical health will be assessed with: surveys measuring depressive and anxiety symptomology; and a wearable fitness tracker (added in year 2) with cortisol testing to measure physiological changes (e.g., resting heart rate and sleep cycle patterns).

**Aim 2:** We will implement a limited feasibility study of partial online yoga delivery via Zoom within the context of the pilot study’s physical education classes to explore scalability to rural communities without access to yoga instructors as well as provide a contingency for COVID-19 school closures.

One session will be held during the PE class period with the yoga instructor teaching remotely to the entire class; another will be held outside of the regular school day with participants attending synchronously from home at a time to be determined by surveying participants’ preferences and availability; both sessions will have a 75% participation rate goal. Qualitative feedback will be gathered from both the yoga instructor and participants on their remote experiences. Remote delivery will also be provided for the control group following the conclusion of the study.

**Aim 3:** Evaluate the study’s school-community-academic partnership at the conclusion of the program using a mixed methods survey. The results will be compared using paired *t* tests with data from the same survey, collected at the end of year 1. The CAB will meet monthly to determine program adjustments. Survey administration and data analysis will occur in summer 2021. The PI will share results with the CAB to determine areas for program refinement and assess need for study continuation with a year 3 expansion.

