estimating. For the first, we will measure mean outcomes by cluster followed by parametric t-tests or non-parametric tests, depending on the distributions of the outcome measures. To account for the variability between gym classes and nested structure of the data, multilevel mixed-effects models will be used for each continuous outcome, with time (T0 & T1) as level 1, students as level 2, and class as level 3. To adjust for baseline pre-treatment values, explanatory variables for each outcome will include grade, gender, prior exposure to yoga at the high school, and survey time point (model 1). To assess the intervention's effect on outcomes, we will use condition (intervention or control) and the interaction between condition and time as predictors (model 2). Effect sizes (ESs) will be calculated as (estimated intervention effect)/ $\sqrt{\text{variance at student level}}$ . Interpretation of ES will determine the gains of the intervention versus control group. To calculate power for this cluster randomized trials that compares two means, we used the "clusterPower" package in R (24). Accounting for clustered design effects, 55 participants with variation in cluster sizes, an assumed low intraclass correlation of 0.001, and within-cluster variation of 5 units, this would provide at least 65% power to detect clinically meaningful effects between the treatment and control arm using two-sided tests at  $\alpha=0.05$ . To maximize test power and precision of estimation considering the few clusters in this study, we will also use wild cluster bootstrap-t procedure to correct our standard errors (9, 47).

A proxy for improved well-being, secondary academic performance outcomes, will also be analyzed descriptively pre- (during week 1) and post-intervention (at the end of week 8) (see table above).

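### The stated 65% power presupposes T1 data from all 55 enrolled students, so 'at least' is unsupported

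*Combined protocol and SAP*

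**What the plan says.** The Study Protocol section plans the second year "with 35 participants in an experimental group, along with 20 students in a control group within the same school", which makes 35 + 20 = 55 students. They sit in two yoga classes and one control class, "therefore creating 3 gym class clusters, which will allow for computer-generated randomization".

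The power statement in the Statistical Analysis Plan rests on "55 participants with variation in cluster sizes", "an assumed low intraclass correlation of 0.001" and "within-cluster variation of 5 units", with two-sided tests at alpha 0.05. It concludes that "this would provide at least 65% power to detect clinically meaningful effects between the treatment and control arm". The footnote to that statement gives power 0.86 if alpha is raised to 0.10. The size of the clinically meaningful effect is not given as a number.

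On loss between T0 and T1, the documents give no rate, no inflation of the sample and no method for missing data. Two places bear on it. The Study Protocol section explains the January to March window by saying that "this timeframe has shown a historical spike in inappropriate student behaviors and absenteeism". Under Aim 1, "Retention and satisfaction of participants, as measured by survey instrumentation from year 1" is cited as a reason to continue the partnership and expand to more classes, but no retention figure is reported.

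**The concern.** The number enrolled and the number in the power calculation are the same, so the power figure describes a trial in which nobody is missing at T1. For a fixed effect, variance, ICC and alpha, power can only fall as students are lost. 'At least' points the other way: it presents the complete-data figure as a minimum.

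Some loss is foreseeable in an 8-week school study, and the sponsor evidently holds year 1 retention information that could have informed an allowance. Loss could also differ by arm. Control students receive the tracker on completing all pre- and post-surveys, whereas the experimental students' incentive depends on 75% attendance.

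What is at stake is how a null result is read. Under Aim 3, results go to the CAB when a year 3 expansion is considered. If the trial outcomes are among them, a reader told that power was 65% or better will take a null result as stronger evidence of no effect than the design warrants.

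**Working it through.** **Inputs from the documents:** 35 and 20 students; 3 classes; ICC 0.001; two-sided alpha 0.05; stated power 65%, and 0.86 at alpha 0.10.

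**Assumptions:** equal class sizes of 55/3 = 18.3 for the design effect; T1 loss of 5% to 25%, spread evenly unless stated; T0–T1 correlations in step 6.

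**1. Reproducing 65%.** This cannot be done, because no effect is stated. The effect is instead back-solved by taking 65% as exact with all 55 analysed.
- Design effect = 1 + (18.33 − 1) × 0.001 = 1.017.
- SE in SD units = √[1.017 × (1/35 + 1/20)] = 0.283.
- Noncentral t with 53 df and power 0.65 needs a noncentrality of 2.389, so d = 2.389 × 0.283 = 0.675 SD. That is 0.675 × 5 = 3.4 units if the 5 is an SD, or 0.675 × √5 = 1.5 units if it is a variance.

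**2. Same effect, with loss L.** Noncentrality = 2.389 × √(1 − L); df = 55(1 − L) − 2; design effect held at 1.017.

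| T1 loss (assumed) | Expected number analysed | Power |
|---|---|---|
| 0% | 55 | 65.0% (by construction) |
| 5% | 52.25 | 62.7% |
| 10% | 49.5 | 60.3% |
| 15% | 46.75 | 57.7% |
| 20% | 44 | 55.1% |
| 25% | 41.25 | 52.3% |

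With 20% lost from the yoga arm only (28 versus 20), power is 61.0%. Losing a single student gives 64.5% (from yoga) or 63.5% (from control).

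**3. Cluster-level degrees of freedom.** Three classes less two arms leaves 1 df; 2 df is shown as a milder case. Re-solving the effect so that complete data give 65%, and again multiplying noncentrality by √(1 − L):

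| Error df | Effect for 65% | 10% loss | 20% loss |
|---|---|---|---|
| 2 | 1.28 SD | 61.3% | 57.3% |
| 1 | 3.37 SD | 62.5% | 59.7% |

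If the effect is instead kept at 0.675 SD with all 55 students, power is about 28% at 2 df and 15% at 1 df.

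**4. The footnote.** A noncentrality of 2.389 with 53 df gives 76.2% at alpha 0.10, not 86%. At 2 df the 65% effect gives 87.1%, and at 1 df 93.8%.

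**5. Anchoring on 0.86 instead.** Power 0.86 at alpha 0.10 with 53 df needs d = 0.78 SD. Power at alpha 0.05 is then 77% with 55 students, 73% with 10% loss and 67% with 20% loss.

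**6. T0–T1 correlation ρ.** For a change-score or condition-by-time contrast, the variance relative to a complete post-only comparison is 2(1 − ρ)/(1 − L). With L = 0.20 and d = 0.675:
- ρ = 0.6: 0.8/0.8 = 1.00, and power is about 65%.
- ρ = 0.7: 0.6/0.8 = 0.75, and power is about 77%.

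**The case against.** The strongest objection is to the tempting next step. A reader might infer that 65% is a ceiling, reached only if nobody is lost. The documents do not support that.

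- The decline in step 2 starts from 65% by construction. Without a stated effect, and with the 5 units undefined, 65% cannot be confirmed even for complete data. Step 5 shows that if the footnote's figure were the reliable one, power would stay above 65% after 20% loss. Nothing in the documents says which figure to trust.
- The power statement compares two means, while the planned mixed model uses both T0 and T1. Step 6 shows that a correlation above 0.6 would more than offset a 20% loss.

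Both arguments defeat 'ceiling'. Neither rescues 'at least', because the plan neither states nor computes a gain from baseline data.

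A reader might also infer that the absenteeism spike means heavy T1 loss. School absence is not the same as a missing T1 survey. Control students, parents and teachers are rewarded for completing surveys, and the parent and teacher SDQ reports do not need the student present. No loss rate can be taken from the documents, so those used here are only illustrations.

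Finally, loss is the smaller threat. With a single control class and an ICC set at 0.001, degrees of freedom matter far more, as the 15% and 28% in step 3 show. The study is also a pilot that openly reports modest power. These points stand and limit the weight of this one. They also mean that replacement text saying 65% holds if all 55 complete would endorse a figure that cannot be verified.

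**Conclusion.** The concern holds in limited form. The power figure treats every enrolled student as analysed, the plan makes no allowance for T1 loss, and 'at least' therefore has no support. This is an omitted planning assumption, not an arithmetic slip.

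Taking 65% as exact for complete data, and holding effect, variance and ICC fixed, 10% to 20% loss costs about 5 to 10 percentage points at the individual level, 4 to 8 with 2 df, and 3 to 5 with 1 df. The direction is the same under each error structure; the size depends on the assumed loss and on the degrees of freedom.

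Separately, the two published power figures do not agree under an individual-level two-sample model. They roughly match at 2 df, which would suit two classes per arm and not the three classes planned. How the software was actually set up cannot be inferred from that.

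**What to change.** In the power statement of the Statistical Analysis Plan:

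- Delete 'at least'.
- State one numerical effect, and say whether the 5 units are an SD or a variance.
- Recompute the alpha 0.05 figure and the footnote's alpha 0.10 figure from that one effect and SD, with error degrees of freedom that reflect three classes.
- Base both on the number of students expected to supply T0 and T1, using year 1 retention and reporting that rate.
- Show the result for complete data and for 10% and 20% loss. If credit is taken for T0–T1 correlation, state the value assumed.

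Do not simply insert 65% as the complete-data figure, because it cannot be verified from what is stated. The change is to wording and calculation only. Enrolment stays at 55, and the only cost is likely to be a less favourable stated power.

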### ***Physical Health Measures.***

Participants enrolled will have their resting heart rate and restorative sleep data tracked and assessed using their Fitbit Inspire HR wristbands. They will be instructed to begin wearing their Fitbit for 1 week prior to starting the intervention to establish baseline data for sleep cycles and resting heart rates; this will also allow the PI to monitor daily data collection to ensure all devices are recording properly and address malfunctions and/or user error prior to the intervention. Once the intervention has begun, the PI will asynchronously and wirelessly connect to their Fitbit data using the Fitabase cloud-based data management platform once weekly to track any changes in duration and quality of restorative sleep and changes in resting heart rate.

### ***Salivary Cortisol Assays.***

Students in both the experimental and control groups will be administered cortisol testing at the beginning of weeks 1 and 4 and the conclusion of week 8, each time prior to the yoga session (or at the beginning of their physical education class, if in the control group). Specifically, students will provide a saliva sample to the school nurse or PI, to be deidentified (using a code key system) before analysis by the CAIRHE Translational Biomarkers Core Lab at MSU. Testing will use the Abcam (ab154996) cortisol in vitro competitive ELISA (Enzyme-Linked Immunosorbent Assay) kit designed for accurate quantitative measurement of cortisol in saliva (sensitivity 0.12 ng/ml). Deidentified cortisol data will be returned to the PI for re-identification using the code key. Comparisons using paired t tests will assess trends and determine usefulness of this measure.

---

 If we increase  $\alpha$  to 0.1, we can reduce the probability of a **Type II error** and increase our power to 0.86 but we are also more likely to commit a **Type I error** (rejecting a true null hypothesis).

Using deidentified participant codes (with the PI retaining access to the code key system), data will be triangulated through observational data, qualitative remarks in participant journals, pre- and post-survey data, heart rate and sleep cycle data, cortisol analyses, and secondary academic and behavioral data.

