**Sources of Materials.** Assessment measures will include the following:

Description of Measure	Source (if applicable)	Timeline for Dissemination	Cronbach’s Alpha/Validity & Reliability
Center for Youth Wellness ACE-Q Self-Reporting Screener for Teens	Burke-Harris & Renschler, 2015	Pre-intervention (in order to determine ACE scores of participants)	Longitudinal testing currently underway to measure content and construct validity/reliability
Generalized Anxiety Disorder Scale (GAD-7)	Spitzer et al., 2006	Pre- and post-intervention	Cronbach’s alpha: .79-.91 Reliability = .85

			Validity = 73.3%
Patient Health Questionnaire for Depressive Symptomology for Adolescents (PHQ-A)	Johnson, 2002	Pre- and post-intervention	Chronbach's alpha = .835 Reliability = .875 Validity = 89.5%
Strengths and Difficulties Questionnaire for ages 11-17 (SDQ Self-Report 11-17), Teachers and Parents Report (SDQ-Teacher/Parent Report 11-17)	Goodman, 2005	Pre- and post-intervention	Chronbach's alpha = .86 Reliability and validity vary according to respondent type and age of child self-reporting
Cortisol salivary assays	Salimetrics Laboratories	Pre (beginning of week 1)-, mid- (week 4) and post-intervention (end of week 8)	Mean accuracy of salivary cortisol testing > 90%
Resting heart rate and sleep cycle data (collected from the wearable fitness tracker, Fitbit Inspire HR)	Fitabase Cloud-Based Data Management System	Pre- (1 week prior to intervention to establish a baseline), mid- (week 4) and post-intervention (at conclusion of week 8) (collected through cloud-based data management system, Fitabase)	Heart rate measure = mean margin of error 5.96% and mean agreement of 91% with ECG data Sleep: Cohen's kappa 0.52-0.53 +/- 0.14; per-epoch accuracy of 69%
Collection of secondary data, including attendance and academic data (MAPS benchmark/progress monitoring standardized assessment scores, attendance, and office referrals)	N/A	Office referrals/behavioral data: Collected 8 weeks prior to study and during 8 weeks of intervention for comparison Attendance data: Collected 8 weeks prior to study and during 8 weeks of intervention for comparison MAPS: Pre- and post-intervention	MAPS Data: Pearson correlation coefficients range from .76-.82 in reading and .82-.86 in mathematics  Other measures: N/A

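### Cortisol is sampled early in the week at baseline and week 4 but late in the week at week 8, so the paired t test, the only analysis named for it, cannot separate position in the week from change over the programme

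*Combined protocol and SAP*

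**What the plan says.** **Sampling times.** Salivary Cortisol Assays places the samples "at the beginning of weeks 1 and 4 and the conclusion of week 8, each time prior to the yoga session". The measures table under Sources of Materials gives "Pre (beginning of week 1)-, mid- (week 4) and post-intervention (end of week 8". The two agree on the first and last samples. The table does not say where in week 4 the middle sample falls.

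**Sessions.** The Study Protocol section states: "Twice weekly 45-minute sessions during the 8-week intervention period will occur within two physical education classes".

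**Who is sampled.** "Students in both the experimental and control groups will be administered cortisol testing"; controls give their sample at the start of their PE class. Planned numbers are "35 participants in an experimental group, along with 20 students in a control group within the same school".

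**Analysis.** For cortisol the text says: "Comparisons using paired t tests will assess trends and determine usefulness of this measure". It does not say whether the tests are run by arm or which pairs of times are compared, and it makes no allowance for day of the week. Separately, the Statistical Analysis Plan says "multilevel mixed-effects models will be used for each continuous outcome, with time (T0 & T1) as level 1", and for the intervention effect "we will use condition (intervention or control) and the interaction between condition and time as predictors (model 2". That text does not name cortisol, and the same section defines T0 and T1 by the baseline and 8-week surveys.

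**The concern.** A paired test reads the mean within-student change as change over the programme. Here the first and last samples differ in two ways: about eight weeks have passed, and the sample has moved from the start of a school week to the end of one. If cortisol before PE differs between those two points of the week, for whatever reason, the paired test counts that difference as programme change.

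Two things are at stake. Aim 1 lists cortisol among the means of assessing the intervention's effect on health, and the cortisol analysis is also meant to inform whether the measure is worth keeping. An artefact of the collection calendar could mislead on both. Unlike a choice of test, collection dates cannot be corrected once the samples have been taken.

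**Working it through.** The documents give no cortisol sample size, power or effect, so there is no planned figure to reproduce. The check has three steps.

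**1. Which comparisons carry the shift.** Let *w* be the late-week minus early-week difference in cortisol, *s* any other change over the January–March window, and *y* the effect of yoga. Using the timing in Salivary Cortisol Assays:

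| Comparison | Position in week | Approximate gap | Expected change, yoga arm |
|---|---|---|---|
| Week 1 to week 4 | early to early | 3 weeks | *y* + *s* |
| Week 4 to week 8 | early to late | almost 5 weeks | *y* + *s* + *w* |
| Week 1 to week 8 | early to late | 8 weeks | *y* + *s* + *w* |

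(*y* and *s* stand for the amount accrued over each interval.) The week 1 to week 4 comparison is free of *w*. The other two are not, and a paired test cannot isolate *w*.

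**2. What a shift would do to a within-arm paired test.** Inputs from the documents: n = 35 and n = 20 (Study Protocol). The two-sided 0.05 level is stated there for the power calculation and is assumed here for the paired test. The documents give neither *w* nor the SD of within-student change, so I assume *b* = *w*/SD of the paired difference, from 0 to 0.4, with *y* = *s* = 0, complete pairs and independent students.

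Rejection probability = P(|T| > t(0.975, n−1)), where T is noncentral t with n−1 degrees of freedom and noncentrality *b*√n. The critical values are 2.032 (34 df) and 2.093 (19 df).

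| Assumed *b* | *b*√35 | Rejects, n = 35 | *b*√20 | Rejects, n = 20 |
|---|---|---|---|---|
| 0 | 0 | 5.0% | 0 | 5.0% |
| 0.1 | 0.592 | 8.9% | 0.447 | 7.1% |
| 0.2 | 1.183 | 21.0% | 0.894 | 13.6% |
| 0.3 | 1.775 | 40.7% | 1.342 | 24.7% |
| 0.4 | 2.366 | 63.3% | 1.789 | 39.7% |

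Simulation of 20,000 trials at *b* = 0, 0.1, 0.2 and 0.3 gave 5.0%, 9.0%, 21.0% and 41.3% for n = 35, in line with the table.

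**3. What a between-arm comparison would do.** Mean change is *y* + *s* + *w* in the yoga arm and *s* + *w* in controls, so the difference is *y*: a common *w* cancels, and so does a common *s*. In simulation (two-sample t test on change scores, 35 v 20, same shift in both arms, clustering ignored) the false-positive rate stayed between 4.9% and 5.1% for *b* from 0 to 0.5. The problem therefore belongs to the paired test, not to every possible analysis of these samples.

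**The case against.** The strongest reply is that the plan may already contain the analysis that removes the shift. Controls are sampled on the same schedule, Aim 1 says year 2 will compare the two groups, and the Statistical Analysis Plan promises a condition-by-time model for every continuous outcome, which cortisol is. This stands in part. If that model was meant to cover cortisol, a shift common to both arms drops out. But the model does not name cortisol, its two time points are the survey times whereas cortisol has three, and cortisol is given a test of its own. Cancellation also needs the same shift in each arm, and the documents do not say that the three classes meet on the same days.

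Second, nothing in the documents shows that cortisol differs across the school week. This stands in full. The size and direction of *w* are unknown, zero included, and the larger rates above come only from the upper part of an assumed range.

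Third, a reader might go further and infer that a common shift, more likely to reach significance with 35 students than with 20, will be reported as a yoga effect. The documents do not support that reading. Nowhere do they plan to compare arms by whether each paired test is significant, and they do not even say that the paired tests are run by arm.

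Fourth, aligning the sampling days leaves every other January–March change inside a paired test. This is correct, and it is why the fix has two parts. The unequal gaps between samples add little on their own: a paired t test does not need equal intervals, and no slope model is specified.

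**Conclusion.** The point holds in a limited form. The schedule moves the sample from early to late in the week between the first two collections and the last, and the one analysis named for cortisol cannot separate that move from change over the programme. How much this matters cannot be told from the documents. The illustrative false-positive rates (9–63% with n = 35, 7–40% with n = 20, against 5%) rest on an assumed shift of 0.1 to 0.4 SD of the paired difference, complete pairs and independent students. They show how sensitive the paired test is, not a demonstrated bias. A between-arm comparison of change would be protected against a shift common to both arms, but whether the plan intends one for cortisol is unclear.

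The priority is low. The study is described as a feasibility study, cortisol is one of several measures to be triangulated, and its analysis is partly about whether to keep it. The change is still worth making, because it costs almost nothing and cannot be made after collection.

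**What to change.** 1. Amend the measures table under Sources of Materials and the Salivary Cortisol Assays section together, so that all three samples are taken at the same session of the week and in the same class period. One option is the last PE session of the Fitbit baseline week, of week 4 and of week 8. All three samples then share a position in the week and are four weeks apart, and the unstated position within week 4 is settled.
2. Name a between-arm comparison of cortisol change, allowing for class, as the main cortisol analysis, and state that the paired t tests are descriptive. Say how the middle sample enters, since the model in the Statistical Analysis Plan has only two time points. This part also deals with other changes over January–March that are common to both arms, which aligning the days does not.

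Cost: two collection dates move, and the number of samples and assays is unchanged. The one drawback is that the school nurse or the investigator must collect saliva during the week in which the Fitbits are being set up.
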